WP4 The Netherlands. For the calculation of the incidence rate of VTE between the two periods specified, i.e. January 2012 to January 2014 and February 2014 to December 2015, we will analyse new users of CHCs (within each calendar window) and assess whether they will develop VTE within one year of CHC initiation. From the analysis of WP1, we will obtain information on a potential change in the proportion of initiators of each generation of CHC between January 2012- January 2014 and February 2014- December 2015. Since we have information about the prescription patterns among new users, we can assess whether the changes observed in the proportions of each generation is associated with changes in the incidence rate of VTE in women initiating oral contraceptive use. Furthermore, we can study the changes in the incidence of VTE within users of different types (and generations) of oral contraceptives. A change in this incidence over time, may indicate that certain preparations are prescribed to low/high risk individuals. Because we have information about the age and socioeconomic status (risk factors of VTE) of these women, we can stratify analyses on these factors.

WP5 Denmark. Incidence rate of VTE will be estimated from the routinely recorded data based on validated algorithms. VTE will be measured using discharge diagnoses recorded in the Danish National Patient Registry.

WP6 United Kingdom. Incidence rates of VTE will be estimated from the routinely recorded data. VTE will be measured by using diagnoses entered into the electronic primary care records by Read codes. It is a hierarchical classification system, linked to the International Classification of Diseases (ICD 10), but more comprehensive.

WP7 Combining findings from WP1-6 to report on trends in oral contraceptive use in the periods before and after the publication of the 2013 EMA review, i.e., January 2012 – January 2014 and February 2014 – December 2015, and the associated changes in the incidence of VTE in the two periods. These results will be combined in the final report for the EMA and in the manuscript for submission for publication.

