For each calendar year, we provide estimates of the number and proportion of new users of each oral contraceptive type and the number and proportion of switchers (from one type to another or to a different dose) overall and stratified by age at initiation of oral contraceptives (18-24, 25-29, 30-34, 35-39, 40-44 and 45-49 years) and socioeconomic status.

In order to assess the effects of the review on initiation as well as on switching of treatment (between January 2012- January 2014 and between February 2014- December 2015), we will perform segmented regression analysis (16).

For our analysis we will use SPSS for Windows, release 23.0.

WP2

Objectives

To obtain the number and proportion of women (within each calendar window) initiating different types of oral contraceptives or per switching pattern using data from the Danish Civil Registration System and the Danish National Prescription Registry.

Methods

Study population

For the Danish drug utilization study, we will obtain information on use of oral contraceptives from the Danish National Prescription Registry, demographic information (age, sex, vital status and migration) from the Danish Civil Registration System and data on income and education at Statistics Denmark in the study period (1 January 2012 to 31

December 2015). Women with no oral contraceptives prescription prior to study start date (from 2010 onwards) will be followed up until they receive their first oral contraceptive dispensation, become 50 years of age, 31 December 2015, or they emigrate or die. The new users are defined as women with no prior prescription of CHC in the two years before.

To investigate switching patterns among prevalent users, individuals will be defined as prevalent users if they had at least one dispensation for an oral contraceptive between 1 July 2011 and 1 August 2015. Prevalent users will be followed from the date of the study start/entry until switch of treatment (defined as prescription of a new type of CHC before expiration of the days supplied of the previous drug), becoming 50 years of age, December 31st 2015, death or emigration, whichever comes first.

Oral contraceptives

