Medication use in the SFK database will be used to approximate the occurrence of VTE by using the first dose of oral anticoagulant, which, in case of DOAC use is specific for VTE or the duration of treatment with Vitamin K antagonists. Incidence of VTE is calculated by following the new users of CHC within each calendar window until they experience a VTE, or up to one year.

We will calculate the incidence among the new users of oral contraceptives in general and per type of oral contraceptive (different types and grouped by generation (second, third and newer generations)).

Analysis

We will tabulate the estimates of the annual incidence of VTE including 95% confidence intervals for each calendar window of the study period.

From segmented regression analysis (WP1), we will obtain information on a potential change in the proportion of initiators of each generation of CHC between January 2012-January 2014 and February 2014- December 2015. Since we have information about the prescription patterns among new users, we can assess whether the changes observed in the proportions of each generation is associated with changes in the incidence rate of VTE in women initiating oral contraceptive use.

Furthermore, we can study the changes in the incidence of VTE within users of different types (and generations) of oral contraceptives. A change in this incidence over time, may indicate that certain preparations are prescribed to low/high risk individuals.

Because we have information about the age and socioeconomic status (risk factors of VTE) of these women, we can stratify analyses on these factors.

For our analysis we will use SPSS for Windows, release 23.0.

WP5

Objectives

To assess changes in the incidence rates of VTE among women of reproductive age overall and by CHC-initiation/switching in Denmark between January 2012-January 2014 and February 2014-December 2015.

Study population

For each calendar year of the study period (1 January 2012 to 31 December 2015) we will identify women who were between 18 and 49 years old. Individuals with no previous record of VTE prior to study entry (from 2002 onwards) will be followed until they are recorded with a VTE, become 50 years of age, 31st of December 2015 or they migrate.

Analysis

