We will estimate the incidence rates of VTE by 10 000 person years at risk in CHC-initiators/switchers before and after the EMA recommendation, including 95% confidence intervals for each calendar year of the study period. We provide overall estimates as well as estimates stratified by age at CHC initiation in oral contraceptive initiators.

For each observation window period (January 2012- January 2014 and between February 2014-December 2015) we will compare the age-standardised incidence rates of VTE against the age standardized VTE incidence rates among initiators/switchers of oral contraceptives in order to evaluate whether overall changes in CHC use is associated with overall changes in incidence of VTE.

Analyses will be performed using SAS version 9.2 or higher.

WP6

Objectives

To assess the incidence rate of VTE among women of reproductive age overall and by initiated CHC in United Kingdom between January 2012- December 2015.

Study population

For the estimate of incidence of VTE in CHC users in UK we will make use of anonymized primary care data. For each calendar year of the study period (1 January 2012 to 31 December 2015) we will identify women who were between 18 and 49 years and have been registered for at least two years prior with one of the general practices that contributed data to THIN. Individuals initiated on CHC with no previous record of VTE prior to study entry (from 2002 onwards) will be followed up until they have their first record of VTE, they become 50 years of age, 31 December 2015 or they de-register with the general practice, whichever comes first.

Analysis

We will tabulate the estimates of incident VTE by 10 000 person years at risk including 95% confidence intervals for each calendar year of the study period among women using CHCs of reproductive age in UK. We provide overall estimates as well as estimates stratified by age, social deprivation (Quintiles of Townsend Deprivation scores), BMI and smoking status.

For each observation window period (January 2012- January 2014 and between February 2014- December 2015) we will calculate the incidence among the new users of oral contraceptives in general and per type of oral contraceptive (different types and grouped by generation (second, third and newer generations)).

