From segmented regression analysis (WP3), we will obtain information on a potential change in the proportion of initiators of each generation of CHC between January 2012-January 2014 and February 2014- December 2015. Since we have information about the prescription patterns among new users, we can assess whether the changes observed in the proportions of each generation is associated with changes in the incidence rate of VTE in women initiating oral contraceptive use.

Furthermore, we can study the changes in the incidence of VTE within users of different types

(and generations) of oral contraceptives. A change in this incidence over time, may indicate that certain preparations are prescribed to low/high risk individuals.

Analysis will be performed using Stata version 14 or higher.

WP7

Outline for the study report

The study report will combine the findings from all 6 work packages. Data from three countries will be used to report on the trends in first ever user prescribing in the two years preceding the relevant Commission Decision January 2012 – January 2014 and the period following the decision February 2014 – December 2015 . Furthermore, using different research strategies, we will report on the changes in the incidences of VTE in the different observation windows, separately for each country. The report will provide evidence regarding the necessity of the recommendation to use safer oral contraceptive preparations as it will show whether the implementation of the recommendation was successful and whether it actually affected the incidence of VTE in the target population.

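### VTE incidence is reported by window and calendar year with no trend adjustment, although prescribing gets segmented regression and the protocol promises to show whether the recommendation affected VTE

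*Protocol*

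**What the plan says.** Section 9.2 names segmented regression in WP1, WP2 and WP3, each time for prescribing: "In order to assess the effects of the review on initiation as well as on switching of treatment". The Abstract limits it in the same way.

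The VTE work packages use rates:

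- **WP4 (Netherlands):** "We will tabulate the estimates of the annual incidence of VTE including 95% confidence intervals for each calendar window of the study period". Its only link to segmented regression is on the exposure side: "From segmented regression analysis (WP1), we will obtain information on a potential change in the proportion of initiators of each generation of CHC".
- **WP5 (Denmark):** VTE rates are given "including 95% confidence intervals for each calendar year of the study period". The comparison is then made within each observation window: "we will compare the age-standardised incidence rates of VTE against the age standardized VTE incidence rates among initiators/switchers".
- **WP6 (UK):** calendar-year VTE rates, and then incidence in new users for each window, overall and by product type and generation.

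The windows are "January 2012 to January 2014 and February 2014 to December 2015". WP7 reports VTE changes between them by country and says of the report: "it will show whether the implementation of the recommendation was successful and whether it actually affected the incidence of VTE in the target population". Section 7 makes the same claim.

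**The concern.** A before/after difference in VTE rates contains any effect of the Decision plus whatever drift was already under way. Segmented regression separates the two by estimating the earlier slope. The protocol uses that method for prescribing but not for the clinical outcome. The report would therefore set a trend-adjusted change in prescribing beside an unadjusted change in VTE, and draw a conclusion about effect from the pair.

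Drift is plausible on the protocol's own description, at least in the Netherlands. There a VTE case is inferred from the first DOAC dose or the duration of vitamin K antagonist treatment, and Section 9.5 says cases are not confirmed. A gradual change in anticoagulant prescribing would move measured VTE without any change in disease. A downward drift would look like a benefit of the recommendation; an upward one could hide a benefit.

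**Working it through.** **The protocol's own count.** The Abstract (Study size) takes 300 000 Danish women, 4 years and 4 VTE per 10 000 per year: 300 000 × 4 × 4/10 000 = 480. This reproduces the stated minimum. It uses a non-user rate, so it serves here only as a scale for precision.

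**Distance between windows.** Number the months of 2012 to 2015 from 0 to 47. The first window is months 0 to 24 (25 months, midpoint 12) and the second is months 25 to 47 (23 months, midpoint 36). The midpoints are 24 months apart.

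**Drift alone.** With a constant yearly trend x and no effect of the Decision, the window rate ratio is about (1+x)². The protocol gives no trend, so x is assumed and varied. With 480 cases spread over the months, the standard error of the log rate ratio is √(1/E1 + 1/E2), where E1 and E2 are the expected cases per window. At x = -5%, E1 = 262 and E2 = 218, giving √(1/262 + 1/218) = 0.092. The last column is the chance that a 95% interval for the ratio excludes 1. It is illustrative, because the protocol specifies no such test.

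| Assumed trend per year | Window rate ratio | Interval excludes 1 (480 cases) |
|---|---|---|
| -3% | 0.94 | 10% |
| -5% | 0.90 | 20% |
| -8% | 0.85 | 44% |
| +5% | 1.10 | 19% |

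**Size of the effect sought.** The Abstract's risk table gives 5-7 per 10 000 for levonorgestrel, norethisterone or norgestimate and 9-12 for drospirenone, gestodene or desogestrel; the midpoints are 6 and 10.5. Assume a 50:50 mix that moves 20 points to the lower-risk group. Before: 0.5 × 6 + 0.5 × 10.5 = 8.25. After: 0.7 × 6 + 0.3 × 10.5 = 7.35. The ratio is 7.35/8.25 = 0.89. Across the ends of the two ranges it runs from 0.84 (5 and 12) to 0.95 (7 and 9). A drift of -5% per year gives 0.90.

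**With a trend term.** A monthly Poisson model with a baseline slope, and level and slope changes at February 2014, was simulated with 480 cases, a -5% yearly trend and no effect. The level-change test rejected in 4.7% of 3000 runs, against 19.8% for the window contrast. The standard error of the log level change was about 0.18, against 0.09. For an immediate 11% fall, power is about 10% for the level change and about 25% for the window contrast.

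**A trap in the new-user cohorts.** The Abstract puts VTE risk at 13-fold in the first three months and 8-fold over the first year. For the year to average 8, months 4 to 12 must average (12 × 8 − 3 × 13)/9 = 6.3. Assume constant monthly initiation from January 2012, one year of follow-up, no trend and no effect. Counting events by calendar month makes early-2012 person-time all recent starters. A segmented model without time since initiation then shows a false baseline slope of -14% per year, a false level ratio of 1.09 and a false slope change of +16% per year. A joint test of level and slope rejects in 13%, 21% and 39% of cases at 480, 960 and 1920 events (the last two totals are assumed).

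**The case against.** The strongest reply is that the protocol sets no two-window test for VTE. It promises rates with confidence intervals, and the ENCePP checklist comment under bias calls the analysis descriptive. A regression model for VTE could also sit in an analysis plan that is not shown. Much of this stands: a reader might infer that the protocol fixes a formal before/after test that credits every trend to the Decision, and the text does not support that. The rejection percentages above describe a test a reader might apply, not a planned one.

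Nor does the protocol look only at two averages. WP5 and WP6 give yearly rates. WP4 and WP6 examine VTE within product types and generations, where a diagnostic or coding drift should appear in every group, and they read a within-type change as selective prescribing rather than as an effect of the Decision. Stratification by age and socioeconomic status, and in the UK by BMI and smoking, removes part of a trend due to risk-factor mix.

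These checks can reveal drift but do not adjust for it. Only 2012 and 2013 lie wholly before the Decision, so yearly rates give two clean baseline points. No method is stated for relating VTE change to generation shares, and two windows per country cannot separate drift from effect. A purely descriptive analysis would be unobjectionable, but the claim in Section 7 and WP7 goes beyond description.

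The objection that a trend model costs power and can mislead in new-user cohorts is also correct. It limits the remedy: the model belongs beside the window rates, not in their place.

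**Conclusion.** The concern holds as a mismatch between analysis and claim. The protocol states a conclusion about effect for VTE but describes only unadjusted rates, while using a trend-adjusting method for prescribing. An existing drift of 3% to 8% per year would alone give a window ratio of 0.94 to 0.85, which overlaps the 0.84 to 0.95 that a 20-point product shift might produce. The 24-month distance follows from the stated windows. The trend sizes, the 50:50 mix and the 20-point shift are assumptions, and the documents give no evidence that a trend exists or in which direction. No stated figure is wrong. The change is worth making because it bears on what Objective 4 can conclude and needs analysis and wording only.

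**What to change.** 1. In WP4, WP5 and WP6, keep the window rates and add a segmented Poisson or negative binomial model of monthly or quarterly VTE counts. Include a person-time offset, age group, calendar slope, and level and slope changes at February 2014.
2. In the new-user cohorts (WP4, WP6 and the Danish initiators), index by month of CHC initiation or adjust for time since initiation, so that high early risk does not create a false break. WP6 follows women to the end of 2015 rather than for one year, so length of follow-up depends on when a woman started; adjustment for time since initiation is the safer choice there.
3. In Section 7 and WP7, limit the claim to a descriptive before/after difference unless the trend-adjusted estimate supports an effect.

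The cost is some programming and text; the event and exposure dates are needed for the planned rates anyway. The trend-adjusted result will be imprecise (standard error about twice that of the window contrast, and about 10% power for an immediate 11% fall at 480 cases). The report should say so and should not read a wide interval as evidence of no effect.

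### In WP4 and WP6 the Objective 4 association step is one before/after contrast with no named measure; it cannot separate a product-mix effect from a secular change in VTE, yet WP7 draws a causal conclusion

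*Protocol*

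**What the plan says.** Objective 4 (Protocol section 8) asks for any measurable association between changes in CHC use and changes in VTE incidence. Section 9.2 handles this as follows.

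- **WP4 (Netherlands), VTE side:** "We will tabulate the estimates of the annual incidence of VTE including 95% confidence intervals for each calendar window of the study period". There are two windows.
- **WP4, prescribing side:** "From segmented regression analysis (WP1), we will obtain information on a potential change in the proportion of initiators of each generation of CHC", the change being the one "between January 2012-January 2014 and February 2014- December 2015".
- **WP4, link between the two:** "we can assess whether the changes observed in the proportions of each generation is associated with changes in the incidence rate of VTE".
- **WP6 (UK):** the linking sentence is repeated, with the share change taken from WP3. VTE in new users is calculated per window, overall and by type and generation. WP6 also tabulates VTE by calendar year but does not bring the years into this step.
- **Within-type rates:** "Furthermore, we can study the changes in the incidence of VTE within users of different types (and generations) of oral contraceptives". Both work packages read such a change as a sign of prescribing to lower- or higher-risk women.
- **Strata:** in WP4, "Because we have information about the age and socioeconomic status (risk factors of VTE) of these women, we can stratify analyses on these factors". WP6 stratifies by age, deprivation, BMI and smoking.
- **WP7:** the report is to show "whether the implementation of the recommendation was successful and whether it actually affected the incidence of VTE in the target population".

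Segmented regression is planned for initiation and switching (WP1 to WP3) and nowhere for VTE. In the ENCePP checklist, item 3.4 answers yes to a specified measure of association and points to section 9.2 (WP 4-6). Item 10.4 answers no to methods for adjusting for confounding, and the comment under Section 7 calls the analysis descriptive.

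**The concern.** One change in shares set beside one change in VTE incidence is a single pair of differences in each of these two countries. Two time points leave no residual degrees of freedom, so no association across time can be estimated. Anything else that moved VTE between the windows, such as coding, diagnostic practice, anticoagulant use (the Dutch VTE proxy) or the risk profile of starters, enters the contrast on the same footing as product mix.

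The quantity that links mix to VTE is the type-specific rate. WP4 and WP6 plan to produce it but do not say it will be combined with the share changes. At stake is the report's main public-health statement, whether the recommendation altered VTE incidence, which would rest on a comparison unable to attribute the change.

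**Working it through.** **1. The plan's own figures.** The Protocol gives no alpha, power or error rate for the association step, so there is none to reproduce. Its one VTE count, for Denmark, does reproduce: 300 000 x 4/10 000 x 4 years = 480. For Dutch new users it says the number of cases is difficult to estimate.

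**2. What section 9.2 supplies for the association step.**

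| | WP4 | WP6 |
|---|---|---|
| VTE in initiators | per window | per window (calendar years tabulated separately) |
| Share change | WP1 segmented regression | WP3 segmented regression |
| Measure of association | none named | none named |
| Time model for VTE | none | none |

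The windows are 25 months (January 2012 to January 2014) and 23 months (February 2014 to December 2015).

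**3. Can the contrast distinguish mix from drift?**

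From the Protocol's risk table: 5-7 per 10 000 for the levonorgestrel group (midpoint 6) and 9-12 for drospirenone, gestodene or desogestrel (midpoint 10.5). Assumed, because the documents give no figure: higher-risk share 50% before and 40% after; 200 000 new-user woman-years per window (range 50 000 to 400 000); an unrelated decline of 5%.

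*True mix effect, no drift*
- Rate before: 0.5 x 6 + 0.5 x 10.5 = 8.25 per 10 000, so 165 events.
- Rate after: 0.6 x 6 + 0.4 x 10.5 = 7.80 per 10 000, so 156 events.
- Rate ratio 7.80/8.25 = 0.945; log = -0.0561.
- SE of the log ratio = sqrt(1/165 + 1/156) = 0.1117; expected z = -0.50.
- Probability that a one-sided 2.5% test is positive = Phi(-1.96 + 0.50) = 7.2%.

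*No mix effect, unrelated 5% decline*
- Same starting rate, 165 events; after, 165 x 0.95 = 156.75 events.
- log 0.95 = -0.0513; SE = 0.1115; expected z = -0.46.
- Probability positive = Phi(-1.96 + 0.46) = 6.7%.

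| Woman-years per window | True mix effect | Unrelated 5% decline |
|---|---|---|
| 50 000 | 4% | 4% |
| 100 000 | 5% | 5% |
| 200 000 | 7% | 7% |
| 400 000 | 11% | 10% |

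Poisson simulation with 400 000 replicates agrees to within about 0.2 percentage points.

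**4. Other assumed settings.** Simulated with 25- and 23-month windows and 100 000 to 300 000 woman-years per year:
- A 10-point shift from a 40% share (7.80 to 7.35 per 10 000) is detected 7% to 14% of the time, and a 20-point shift 18% to 44%.
- With no mix effect and 8 per 10 000 before, an unrelated rate ratio of 0.95 gives a concordant positive 6% to 12% of the time, and 0.90 gives 15% to 35%.

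More data make the crude test positive more often in both situations without telling them apart.

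**5. What the decomposition gives at the inputs of step 3.** Mix component = sum over types of (share change x type-specific rate) = (-0.10 x 10.5) + (0.10 x 6) = -0.45 per 10 000. The within-type remainder is the total change minus this. With a true mix effect alone, the total is -0.45 and the expected remainder is 0. With the unrelated decline and equal risks, the mix component is 0 and the remainder is 0.05 x 8.25 = -0.41 as a change. The two situations that looked alike in step 3 now fall into different components.

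**The case against.** **The missing formula may be in a statistical analysis plan.** That plan is not shown, and a protocol may leave model detail to it. This stands as far as the absence of a formula goes. It does not answer the rest: the checklist says section 9.2 already specifies the measure, the comparison that the Protocol does describe is a before/after contrast, and the causal sentence is in the Protocol.

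**A same-sign rule.** A reader might infer that the plan declares an association whenever share and VTE move the same way, which chance alone would produce half the time. The documents state no such rule. They plan 95% confidence intervals, and a criterion based on the interval for the rate ratio gives about 2.5% false concordance (5% two-sided) when there is no drift. The difficulty is drift, not a coin toss.

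**Two windows in every country.** A reader might extend the point to all three countries. Denmark does not fit: the WP5 comparison uses no generation shares, and WP5 gives VTE rates "before and after the EMA recommendation, including 95% confidence intervals for each calendar year of the study period". WP6 also tabulates by calendar year. Only WP4 limits its VTE tabulation to the windows.

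**The decomposition as a more powerful test.** Its mix component looks far more precise: -0.45 with SE about 0.09, against SE about 0.90 for the crude difference. But the pooled woman-years are 180 000 and 220 000, so the SE of the rate difference is sqrt(10.5/180 000 + 6/220 000), scaled to 0.925 per 10 000, and z = 4.5/0.925 = 4.9. With shares taken as known, the size of the shift cancels, and a 1-point shift would give the same z. That is evidence that the types differ in risk, not that incidence changed, and the component could be significant while VTE rose. The two precisions must not be compared as power for one question.

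**The ingredients are already planned.** This is true, and it is why the change is cheap. The Protocol does not say they will be combined.

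**Conclusion.** The concern holds for WP4 and WP6. The association step is one before/after contrast per work package with no named measure, contrary to checklist item 3.4. It cannot separate product mix from a concurrent change in VTE and so does not support the causal conclusion in WP7.

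At 200 000 woman-years per window, a crude one-sided test is positive about 7% of the time under either explanation (4% to 11% across 50 000 to 400 000). These percentages rest on assumed woman-years, shares, shift and drift. The structural point does not: no choice of those inputs lets a single before/after difference be attributed to one cause.

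**What to change.** In the analysis text of WP4 and WP6, replace the linking sentence with a stated decomposition.

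1. Within age bands (plus socioeconomic status in the Netherlands; deprivation, BMI and smoking in the UK), estimate type- or generation-specific VTE rates in initiators.
2. Split the before/after change in initiator VTE incidence into a mix component, the sum over types of share change x type-specific rate, and a within-type remainder.
3. Report both with 95% confidence intervals alongside the total observed change, not in place of it.
4. State that a significant mix component shows what the share shift would be expected to contribute given the type-specific rates, not that VTE incidence fell, and that it carries any residual confounding and channelling in those rates.
5. Reword the WP7 conclusion to match these limits, and bring checklist item 3.4 into line with section 9.2.

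Cost: protocol wording and a little extra analysis on quantities already planned, with no new data. The downside is dependence on adequately adjusted type-specific rates, to be listed in section 9.5.
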